6.4 COVARIATES

Patients with mRCC will be grouped according to the physicians risk assessment at time of inclusion in the study and by their prognosted risk according to the Motzer score.

Patients suffering from MCL will be grouped according to the physicians risk assessment at time of inclusion in the study and by prognosted risk according to the MIPI score (at time of inclusion and at time of primary diagnosis).

Patients with GIST will be grouped according to the physicians risk assessment at time of inclusion in the study and by their prognosted risk according to Fletcher risk table at time of primary diagnosis.

6.4.1 Motzer score

Motzer score

According to the Motzer score five risk factors are defined: low Karnofsky performance status (< 80%), high LDH (> 1.5 times upper limit of normal \equiv > 300 U/L), low hemoglobin (< lower limit of normal \equiv < 13 g/dL for male patients, < 11.5 g/dL for female patients), high corrected serum calcium (> 10 mg/dL) and time from diagnosis to start of Torisel® or Sutent® treatment less than one one year. A patient without any risk factor present at baseline visit belongs to the favorable-risk group, one with one or two risk factors present at baseline belongs to the intermediate-risk group and one with three or more risk factors present at baseline belongs to the poor-risk group.

The corrected serum calcium value will be computed from the values of serum calcium and serum albumin according to the following formula:

Corrected Serum Calcium (mg/dL)

= Calcium (mmol/L) * 4.008 - 0.707 * (Albumin (g/L) / 10 - 3.4).

Modified Motzer score

The modification of the Motzer score adds one further risk factor: at least 2 sites of organ metastases. The assignment to the risk groups and the calculation of corrected serum calcium remains unchanged. Within this study modified Motzer score was only determined for 1^{st} line patients. Only two categories were analyzed " $\geq 3 = \text{poor}$ " and "< 3 = non poor".

Motzer score for previously treated patients

The Motzer score for previously treated patients is based on the three risk factors: low Karnofsky performance status (< 80%), low hemoglobin (< lower limit of normal \equiv < 13 g/dL for male patients, < 11.5 g/dL for female patients) and high corrected serum calcium (> 10 mg/dL). The score is only defined for patients with at least one previous systemic treatment of RCC. A patient is assigned to the favourable-risk groups, if no risk

factor is present, to the intermediate-risk group, if one risk factor is present and to the poor-risk, if two or three risk factors are present.

6.4.2 Mantle Cell Lymphoma International Prognostic Index (MIPI)

MIPI score is defined as

Score = $0.0353 * age (yrs) + 0.6978 * [ECOG > 1 {yes/no}] + 1.367*log₁₀(LDH/ULN LDH) + 0.9393*log10(Leukocyte count [/µl])$

Low risk if Score < 5.7

Intermediate risk if $5.7 \le \text{Score} < 6.2$

High risk if $6.2 \le Score$

If all data necessary to compute MIPI score are available, the calculated risk will be used for analyses of current MIPI. Otherwise and for the time of primary diagnosis the value documented by the physician will be used.

6.4.3 Fletcher Risk Table (NIH Risk Table)

The risk of recurrence or metastasis of a primary GIST may be prognosted according to the Fletcher Risk Table (Fletcher et al, 2002):

Risk prognosis	Size (largest diameter) of primary	Mitotic Count (per 50 HPF)
	tumor	
Very low risk	< 2 cm	≤ 5
Low risk	$\geq 2 - \leq 5$ cm	≤ 5
Intermediate risk	< 5 cm	6 - 10
Intermediate risk	$\geq 5 - \leq 10 \text{ cm}$	≤ 5
High might	> 5 cm	> 5
High risk	> 10 cm	any

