5.4 SUBGROUPS

Effectiveness analyses of mRCC patients will be repeated for subgroups based on physician's prognosis of patients risk and for the risk groups according to Motzer score, modified Motzer score and Motzer score for pretreated patients.

For subjects in first line Torisel[®] therapy with poor prognosis according to modified Motzer the following variables will be analyzed: age, gender, Karnofsky index, organs with metastases, prior surgeries, duration of disease, histology, progression free survival and overall survival.

Effectiveness analyses of MCL patients will be repeated for subgroups based on the risk groups according to MIPI (Mantle cell lymphoma international prognostic index).

Effectiveness analyses of GIST patients will be repeated for subgroups based on physician's prognosis of patients risk and for the risk groups according to Fletcher Risk Table.

[figure not shown]

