8.1.2 Analysis Of Survival Data

OS, PFS and treatment duration will be analyzed using Kaplan-Meier plots. Median, 25% and 75% survival times with confidence intervals for OS and PFS will be presented. For stratification according to physician's prognosis and for risk groups according to Motzer score/MIPI/Fletcher risk table, log-rank tests will be performed.

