1.3-1.4	Tumor anamnesis - other information	GIST	SAFETY, EAS	.1 Frequency table for size of primary tumor, sample statistics for number of mitoses, frequency table for primary mutation analysis performed?, frequency table for type of KIT-mutation .2 Frequency table for mutation analysis performed in recidive?, frequency table for type of mutation
CCI				
1.3-3	ECG	mRCC, GIST	SAFETY, EAS	Frequency tables for normal/abnormal ECG by time window

Table No.	Title	Treatment/ Indication	Analysis set	Description
CCI				

Table No.	Title	Treatment/ Indication	Analysis set	Description
CCI				
				, number of transplantations, R0 resection reached

Table No.	Title	Treatment/ Indication	Analysis set	Description
CCI				

Table No.	Title	Treatment/ Indication	Analysis set	Description
CCI				
2	Effectiveness			
2.1	Response to therapy			
2.1-1	Course of response to therapy	All	EAS	Frequency table by time window (in total and by patient risk groups)

Table No.	Title	Treatment/ Indication	Analysis set	Description
2.1-2	Best response	All	EAS	Frequency table for best response in total and confirmed / not-confirmed (the latter not for Torisel® MCL); Frequency table for best response excluding patients "not assessable" only for MCL Listing of reasons for not assessable best response; Frequency table for best response by patient risk groups
2.1-3	Used diagnosis technique	All	EAS	CT, Thorax X-ray, MRT, Ultrasonic testing, PET, Bone scan, Clinical (by time window and for best response)
2.2	Overall survival			
2.2-1	Kaplan-Meier estimates for Overall survival	All	EAS Sequence analysis	Time to 25%, median and 75% survival with confidence intervals incl Kaplan-Meier curve on all patients
2.2-2	Kaplan-Meier estimates for Overall survival by patient risk groups	mRCC	EAS	 .1 Physicians prognosis of patients risk .2 Risk groups according to Motzer score .3 Risk groups according to modified Motzer score .4 Risk groups according to Motzer score for pretreated patients .5 by treatment sequence .6 by treatment and treatment line. .7 1st line patients by risk (poor vs. non-poor) .8 by LDH ≤ 300 U/l vs > 300 U/l incl. Log-ranktest and Kaplan-Meier curves

Table No.	Title	Treatment/ Indication	Analysis set	Description

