2.2-2	Kaplan-Meier estimates for Overall survival by patient risk groups	MCL	EAS	.1 Risk groups according to MIPI score at time of primary diagnosis .2 Risk groups according to current MIPI score .3 2 nd and 3 rd line .4 2 nd to 4 th line .5 4 th line and beyond .6 5 th line and beyond .7 Patients with OR (CR+PR) .8 Patients with (MR + SD) .9 Patients with clinical benefit (CR+PR+MR+SD) .10 Patients ≤ 65 vs. patients > 65 yrs. including Kaplan-Meier curves .1 OS all patients excluding "not assessable" patients .2 OS patients with OR (CR+PR) vs. (MR+SD) vs. PD .3 OS patients with clinical benefit (CR+PR+MR+SD) vs. PD .4 OS Temsirolimus 2 nd to 4 th line (1 − 3 prior therapies) vs. 5 th line and beyond (≥ 4 prior therapies) .5 OS 2 nd to 3 rd line Temsirolimus (1 − 2 prior therapies) vs. 4 th line and beyond (≥ 3 prior therapies)
2.2-2	Kaplan-Meier estimates for Overall survival by patient risk groups	GIST	EAS	.1 Risk groups according to Fletchers risk table .2 Risk groups according to physician's prognosis
2.2-3	Frequency table of patients status by time window (survival phase)	All	EAS	
2.3	Progression free survival			
2.3-1	Kaplan-Meier estimates for Progression free survival	All	EAS Sequence analysis	Time to 25%, median and 75% survival with confidence intervals including Kaplan-Meier curve on all patients

Table No.	Title	Treatment/ Indication	Analysis set	Description
2.3-2	Kaplan-Meier estimates for Progression free survival by patient risk groups	mRCC	EAS	.1 Physicians prognosis of patients risk .2 Risk groups according to Motzer score .3 Risk groups according to modified Motzer score .4 Risk groups according to Motzer score for pretreated patients .5 by treatment sequence .6 1st line patients .7 1st line patients by risk (poor vs. non-poor) .8 2nd line vs. higher lines .9 2nd vs. 3rd line vs. higher lines .10 patients ≤ 65 yrs vs. > 65 yrs .11 by LDH low (≤ 300 U/l) vs high (> 300 U/l) .12 by histology (clear cell vs. other) Kaplan-Meier curves incl Log-Rank-Test .1 PFS 1st line vs. 2nd line and higher .2 PFS 1st line vs. 2nd line vs. 3rd line and higher .3 PFS ≤ 65 yrs vs. > 65 yrs .4 PFS LDH low (≤ 300 U/l) vs high (> 300 U/l) .5 PFS clear cell histology vs. other histology

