Description Table No. Title Treatment/ **Analysis set** Indication .1 Risk groups according to MIPI score at time of 2.3-2 Kaplan-Meier estimates for Progression free MCL EAS survival by patient risk groups primary diagnosis .2 Risk groups according to current MIPI score .3 2nd and 3rd line .4 2nd to 4th line .5 4th line and beyond .6 5th line and beyond .7 Patients with OR (CR+PR) .8 Patients with MR + SD .9 Patients with clinical benefit (CR+PR+MR+SD) Kaplan-Meier curves incl. Log-Rank-Test .1 PFS all patients excluding "not assessable" patients .2 PFS patients with OR (CR+PR) vs. (MR+SD) .3 PFS patients with clinical benefit (CR+PR+MR+SD) .4 PFS Temsirolimus 2^{nd} to 4^{th} line (1-3) prior therapies) vs. 5^{th} line and beyond (≥ 4 prior therapies) .5 PFS 2^{nd} to 3^{rd} line Temsirolimus (1 – 2 prior therapies) vs. 4th line and beyond (≥ 3 prior therapies) .1 Risk groups according to Fletchers risk table Kaplan-Meier estimates for Progression free EAS 2.3-2 **GIST** survival by patient risk groups .2 Risk groups according to physician's prognosis Physician's global assessment 2.4 Frequency table by time windows and for the last 2.4 Physician's global assessment of effectiveness mRCC **EAS** documented visit: total and by physician's prognosis of patients risk and by risk groups according to Motzer score, modified Motzer score and Motzer score for pretreated patients. Frequency table by time windows and for the last 2.4 Physician's global assessment of effectiveness MCL EAS documented visit: total and by risk groups according to MIPI score at time of primary diagnosis and

PFIZER CONFIDENTIAL

according to current MIPI score.

Table No.	Title	Treatment/ Indication	Analysis set	Description
2.4	Physician's global assessment of effectiveness	GIST	EAS	Frequency table by time windows and for the last documented visit: total and by physician's prognosis of patients risk and by risk groups according to Fletchers risk table.
2.5	Course of Karnofsky performance status scale			
2.5	Course of Karnofsky performance status scale	mRCC, GIST	EAS Sequence analysis for mRCC	Sample statistics by time windows and for the last documented visit, including absolute and relative differences to baseline (in total and by patient risk groups)
2.5	Course of ECOG performance status and B-symptoms			

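### As printed, the Fletcher risk table for GIST in SAP 6.4.3 gives a tumour of exactly 5 cm two classes or none, and has no row for tumours of 5 cm or less with more than 10 mitoses

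*SAP*

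**What the plan says.** SAP 6.4.3 introduces the GIST risk groups with the words "The risk of recurrence or metastasis of a primary GIST may be prognosted according to the Fletcher Risk Table" and defines them by the largest diameter of the primary tumour and the mitotic count per 50 high-power fields. The printed rows amount to this:

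| Row | Class | Size | Mitoses |
|---|---|---|---|
| 1 | Very low | < 2 cm | ≤ 5 |
| 2 | Low | ≥ 2 to ≤ 5 cm | ≤ 5 |
| 3 | Intermediate | < 5 cm | 6 to 10 |
| 4 | Intermediate | ≥ 5 to ≤ 10 cm | ≤ 5 |
| 5 | High | > 5 cm | > 5 |
| 6 | High | > 10 cm | any |

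SAP 5.4 puts the table to use: "Effectiveness analyses of GIST patients will be repeated for subgroups" formed from the physician's prognosis and "for the risk groups according to Fletcher Risk Table". In SAP 9, the GIST version of Table 2.2-2 (OS) lists the strata as "1 Risk groups according to Fletchers risk table .2 Risk groups according to physician's prognosis". Table 2.3-2 (PFS) does the same, and Table 2.4 splits the physician's global assessment in the same two ways. Tables 2.1-1 and 2.1-2 report response by patient risk group. SAP 8.1.2 adds that "for risk groups according to Motzer score/MIPI/Fletcher risk table, log-rank tests will be performed", and SAP 8.1.1 plans Cohen's kappa between the risk scores and the physician's prognosis.

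**The concern.** A stratified Kaplan-Meier analysis, a log-rank test and a kappa each need every patient in exactly one class. A table that gives some patients two classes and others none cannot be programmed as written, so the programmer has to supply a rule that the SAP does not contain. The choice could differ between the repeated interim analyses and the final one. It also decides whether a patient at the 5 cm boundary counts as low or intermediate, and whether a small tumour with a very high count enters any risk group. On the printed rows, a 4 cm tumour with 8 mitoses is intermediate while a 4 cm tumour with 20 mitoses has no class.

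**Working it through.** The plan gives no figure to reproduce; the check is logical. The inputs are the six rows above, with size *s* in cm and mitoses *m* as a whole number. The table works only if every pair (*s*, *m*) satisfies rows of exactly one class.

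**Exactly 5 cm, *m* ≤ 5.** Row 2 requires 2 ≤ 5 ≤ 5, which is true. Row 4 requires 5 ≤ 5 ≤ 10, which is also true. Result: low and intermediate.

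**Exactly 5 cm, *m* from 6 to 10.** Row 3 requires 5 < 5, false. Row 5 requires 5 > 5, false. Row 6 requires 5 > 10, false. Rows 1, 2 and 4 fail because *m* > 5. Result: no class.

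**5 cm or less, *m* > 10.** Rows 1, 2 and 4 fail because *m* > 5. Row 3 fails because *m* > 10. Rows 5 and 6 fail because *s* ≤ 5. Result: no class.

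**Everything else.** The rows were evaluated on a grid of sizes from 0.1 to 20.0 cm in steps of 0.1 and counts from 0 to 50, that is 200 × 51 = 10,200 cells.

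| Region | Cells | Result |
|---|---|---|
| 5.0 cm, 0 to 5 mitoses | 1 × 6 = 6 | two classes |
| 5.0 cm, 6 to 10 mitoses | 1 × 5 = 5 | no class |
| ≤ 5.0 cm, 11 to 50 mitoses | 50 × 40 = 2,000 | no class |
| all other cells | 10,200 − 2,011 = 8,189 | one class |

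These are cells of a logic check, not patients, and their proportions say nothing about frequency. Tumours above 10 cm with more than 5 mitoses satisfy rows 5 and 6, but both are high, so there is no conflict. Every cell above 5 cm with more than 10 mitoses is high.

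**Is the matter settled elsewhere?** SAP 6.4.2 gives the MIPI a fallback to the value documented by the physician. SAP 7 gives assignment rules for the three Motzer scores and otherwise leaves missing values unreplaced. Neither covers the Fletcher table. No section states which class prevails in an overlap or what happens to a patient without a class.

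**The case against.** A reader might infer that GIST patients with high mitotic counts drop out of the risk-stratified OS and PFS. The documents do not support that, for several reasons.

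- The gap above 10 mitoses may not be in the plan. The available text was read from PDF, and the high-risk block is visibly damaged (its label is garbled), so a row may be missing. This stands. It does not reach the two problems at exactly 5 cm, which come from the inequality signs in rows that are present; an extra row for counts above 10 would leave both in place. Those signs should still be checked in the same original table.
- Even as printed, only tumours of 5 cm or less lose their class. Larger ones with high counts are high risk.
- Dropping out is an inference. The SAP is silent on unclassified patients. They remain in the effectiveness set, the unstratified Tables 2.2-1 and 2.3-1 and the physician-prognosis strata.
- Size may be recorded in categories. SAP 9, Table 1.3-1.4, plans a "Frequency table for size of primary tumor, sample statistics for number of mitoses", and SAP 8.1.1 uses frequency tables for categorical data. If so, whether an exact 5 cm value ever occurs depends on CRF categories that the documents do not show. Nothing in the documents shows that 5 cm is a common recorded value. The gap above 10 mitoses, if real, would remain.
- The stakes are modest. The protocol calls the evaluation purely descriptive, SAP 4 has no hypotheses or decision rules, and the table grades the primary tumour at diagnosis (SAP 6.4) in patients who enrol with unresectable or metastatic disease.

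These points limit the consequence. They do not make the printed table usable as a classification.

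**Conclusion.** The point holds in limited form. On the printed rows, one combination has two classes (exactly 5 cm, 5 or fewer mitoses) and one has none (exactly 5 cm, 6 to 10 mitoses). A third region has none (5 cm or less, more than 10 mitoses), subject to the original SAP confirming that no row was lost.

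The effect is restricted to the Fletcher-stratified GIST effectiveness analyses, the associated log-rank tests and the kappa against physician's prognosis. The number of patients affected is unknown, because the documents give neither the number of GIST patients nor a distribution of size by mitotic count; for the 5 cm boundary it also depends on how the CRF records size. No direction of bias can be stated. The conclusion assumes that the inequality signs were read correctly and that mitoses are whole counts. It is a rule that cannot be applied as written in a secondary descriptive analysis, worth correcting because the correction is small.

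**What to change.** First compare SAP 6.4.3 with the original document and with the classification it cites. Then use one cut at 5 cm in all rows and make sure that every count above 10 has a class. One version that closes the table, placing 5 cm in the lower band, is:

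| Size | ≤ 5 mitoses | 6 to 10 | > 10 |
|---|---|---|---|
| < 2 cm | very low | intermediate | high |
| ≥ 2 to ≤ 5 cm | low | intermediate | high |
| > 5 to ≤ 10 cm | intermediate | high | high |
| > 10 cm | high | high | high |

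Each cell holds exactly one class. Two entries are choices to be confirmed against the cited source: putting exactly 5 cm in the lower band, and classing 5 cm or less with more than 10 mitoses as high, which follows the table's own ordering. If the CRF records size in categories, map those categories to the table explicitly. Add a check to the derivation program that every size-by-count combination, or every CRF size category by count, returns exactly one class.

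The cost is a few words in one SAP table and one derivation, with no new data.

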7 HANDLING OF MISSING VALUES

Generally, missing values still missing after performing quality improvement measures (edit checks, queries) were performed, will not be replaced

For determining the risk groups according to Motzer score, modified Motzer score and Motzer score for pretreated patients the following procedures will be kept to:

- If at least three (two for Motzer score for pretreated patients) risk factors are present, missing values for the remaining can be ignored and the patient will be assigned to the poor risk group.
- If the calcium value is given, but the albumin value is missing, than calcium will be interpreted as a risk factor if the calcium value is above 11 mg/dL.
- If the hemoglobin value is missing, but a clinically significant low hemoglobin value or anemia is documented as comorbidity, than this will be interpreted as a risk factor present.
- If the LDH value is missing, but a clinically significant high LDH value is documented as comorbidity, than this will be interpreted as a risk factor present.

With the protocol amendment including mRCC patients being treated with axitinib some additional information was asked for in the CRF. This implies missing values for patients documented under earlier versions of protocol and CRF. The percentage of missings due to this reason will not be reported in tables extra. With amendment VI interim treatment with non-Pfizer products was included. This data will only be analyzed for patients documented under amendment VI.

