6.2 SAFETY ENDPOINTS

Variable	Role	Operational definition
Incidence and severity of treatment-emergent adverse events	Safety outcome	
Discontinuation due to adverse event	Safety outcome	
Discontinuation from Study	Safety outcome	
Serious adverse events	Safety outcome	
Death	Safety outcome	either "intensity according to NCI-CTC-criteria = grade V fatal" or "outcome = exitus" or "event term = death"
Laboratory values (if available)	Safety outcome Subgroup identifier	Hemoglobin, calcium, albumin, LDH, creatinine, ALT, AST, alkaline phosphatase, total bilirubin, TSH, fT3, fT4, hematocrit, phosphate, HbA1c, glucose, neutrophils, lymphocytes, monocytes, eosinophils, basophils, sodium, potassium, magnesium, cholesterol, triglycerides
Global tolerability assessment	Safety outcome	

PFIZER CONFIDENTIAL

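### SAP section 7 completes a partly missing Motzer or modified Motzer score only towards poor risk, so incomplete patients who are certainly non-poor or certainly intermediate get no group

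*SAP*

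**What the plan says.** SAP section 6.4.1 sets out three scores.

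- **Motzer:** "According to the Motzer score five risk factors are defined". None present is favorable, one or two is intermediate, three or more is poor.
- **Modified Motzer:** a sixth factor is added and the score is used for first-line patients only. "Only two categories were analyzed": poor at three or more, non-poor below three.
- **Motzer for previously treated patients:** three factors. None present is favourable, one is intermediate, two or three is poor.

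SAP section 7 starts from a general rule of no replacement ("Generally, missing values still missing after performing quality improvement measures" stay missing). For the Motzer scores it then gives one rule that closes a score with factors still missing. When the known factors alone already reach the poor-risk threshold (three, or two in the pretreated score), the consequence is that "missing values for the remaining can be ignored and the patient will be assigned to the poor risk group". Three further rules cover a single factor: calcium without albumin, missing hemoglobin with documented anemia, and missing LDH with a documented high value. Each says only when the factor counts as present.

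The visible text does not say what happens to patients who remain unclassified. By contrast, section 6.4.2 gives the MIPI a fallback to the physician's documented value.

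**The concern.** The plan accepts logical certainty as a reason to classify an incomplete patient, but only at the poor end. In the six-factor score, a patient with one factor present, one missing and four absent ends with a count of one or two, so is non-poor whatever the missing value is. In the five-factor score the same pattern (three absent) is certainly intermediate. Neither has an assignment rule.

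The risk groups feed the OS and PFS tables by risk group in SAP section 9 (Tables 2.2-2 and 2.3-2 for mRCC), including the row "1st line patients by risk (poor vs. non-poor" groups), the log-rank tests in section 8.1.2, the effectiveness subgroups in section 5.4 and the kappa statistic in section 8.1.1. If the poor group keeps incomplete patients while the other groups are close to complete-case, the groups compared have been selected differently. Two programmers could also fill the silence differently: one might leave these patients out, another might count missing as absent, which can only under-count poor risk.

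**Working it through.** The documents state no figure for this point, so there is none to reproduce. The check has two parts.

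**1. Which incomplete patterns are certain?** Each factor is present, absent or missing. The lowest possible score is the number present; the highest is present + missing. Counting every pattern with at least one factor missing:

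| Score | Incomplete patterns | Certainly poor (rule exists) | Certainly non-poor (no rule) | Undetermined |
|---|---|---|---|---|
| Motzer, 5 factors | 211 | 35 | 35, of which 20 certainly intermediate | 141 |
| Modified, 6 factors | 665 | 191 | 51 | 423 |
| Pretreated, 3 factors | 19 | 3 | 3, none certainly favourable or intermediate | 13 |

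The gap is therefore real for the first two scores. In the pretreated score no incomplete pattern fixes favourable or intermediate, so leaving those patients unassigned is correct.

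**2. How much could it matter?** All inputs here are assumptions: six independent factors, each present with probability 0.3, and LDH, hemoglobin and calcium each missing at random. The single-factor substitution rules are not modelled. Worked at 10% missing:

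- True non-poor: 0.7^6 + 6·0.3·0.7^5 + 15·0.3^2·0.7^4 = 0.1176 + 0.3025 + 0.3241 = 0.7443 (from unrounded terms). True poor: 0.2557.
- Classified poor (three or more observed present; laboratory factors observed present with probability 0.3·0.9 = 0.27, the others 0.3): 0.2283.
- Non-poor with complete data: 0.7443·0.9^3 = 0.5426.
- Certainly non-poor, complete or not (present + missing at most 2; a laboratory factor is present or missing with probability 1 − 0.7·0.9 = 0.37): 0.6774.
- Poor share as written: 0.2283/(0.2283 + 0.5426) = 29.6%.
- Poor share with a matching rule: 0.2283/(0.2283 + 0.6774) = 25.2%.
- Certain class but unassigned: 0.6774 − 0.5426 = 13.5%.
- Kept as written: 0.2283/0.2557 = 89% of truly poor patients, but 0.5426/0.7443 = 73% of truly non-poor patients. With the matching rule the second figure is 0.6774/0.7443 = 91%.

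The same calculation across the range:

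| Prevalence (true poor) | Missing per laboratory factor | Poor share as written | With matching rule |
|---|---|---|---|
| 0.3 (25.6%) | 10 / 20 / 30% | 29.6 / 34.6 / 40.8% | 25.2 / 25.0 / 24.8% |
| 0.4 (45.6%) | 10 / 20 / 30% | 51.1 / 57.2 / 64.0% | 46.2 / 47.0 / 48.0% |

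At prevalence 0.3, unclassified patients fall from 22.9 / 41.7 / 56.9% to 9.4 / 19.1 / 29.0%.

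**Informative missingness.** Now let a laboratory factor be missing in 30% of patients when present and in 5% when absent:

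| Score, prevalence | True | As written | Matching rule |
|---|---|---|---|
| 6 factors, 0.3 | 25.6% | 24.8% | 19.8% |
| 6 factors, 0.4 | 45.6% | 46.7% | 39.3% |
| 5 factors, 0.4 | 31.7% | 30.2% | 23.5% |

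The direction of the distortion is therefore not fixed, and in these cases the matching rule moves the share further from the truth. Bounds still hold. In the first row, 17.6% of all patients are classified poor and 11.3% are undetermined, so the poor share lies between 17.6% and 17.6 + 11.3 = 28.9%, which contains 25.6%.

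**The case against.** The strongest reply is that section 7 never excludes these patients. Under section 6.4.1, a patient with one factor present, one missing and the rest absent meets the intermediate or non-poor definition whatever the missing value is, so nothing has to be replaced. That is a sensible reading, but section 7 lists the procedures to be followed for incomplete scores and names only the poor case. A programmer following it literally would leave the patient out.

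Several stronger readings are tempting, and the documents do not support them.

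- **That the rule misclassifies patients as poor.** It does not: three present factors mean poor whatever else is missing.
- **That the first-line temsirolimus poor-prognosis description in section 5.4 ("therapy with poor prognosis according to modified Motzer the following variables will be analyzed") is distorted.** A matching rule moves nobody into or out of the poor group, so that subgroup is unchanged.
- **That incomplete patients can only become poor.** A documented anemia or high LDH can complete a score at one or two factors, which is intermediate.
- **That the poor share is inflated.** This holds among classified patients if missingness is unrelated to the factors. It can reverse otherwise, and as a share of all patients the classified-poor fraction is too low (22.8% against 25.6% in the worked case).

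The amount of missing data is also unknown. The label "Laboratory values (if available") in section 6.2 concerns safety endpoints, laboratory values are scheduled at baseline, and section 7 applies after queries. Still, section 7 itself provides for missing albumin, hemoglobin and LDH. Some baseline tables are redacted, so a row for unknown risk cannot be ruled out there. Finally, the registry is descriptive, with no hypotheses or decision rules, which limits the stakes.

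**Conclusion.** The point stands as a one-sided completion rule for the five-factor and modified scores. It rests on the text and on the pattern count, without any assumption about the data. What is certain is that some patients with a known class have no stated assignment, and that the comparator groups are selected differently from the poor group if section 7 is followed literally.

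The size is conditional. With random missingness of three laboratory factors in 10 to 30% of patients and prevalence 0.3, about 13 to 28% of patients would lose a certain class, and the poor share among classified patients would read 30 to 41% instead of 26%. These are illustrations from assumed inputs. A reader might infer a proven upward bias in poor risk or a problem in all three scores; neither follows. The change is worth making before the final analysis, but it does not threaten the registry's main descriptive results.

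**What to change.** In SAP section 7, add:

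- **(a) Modified Motzer:** if factors present + factors missing ≤ 2, assign non-poor.
- **(b) Five-factor Motzer:** if at least one factor is present and present + missing ≤ 2, assign intermediate.
- **(c) All others still undetermined:** leave unclassified, do not treat missing as absent, and show them as a separate row in the risk-group tables. Give any reported poor share with a lower bound (all undetermined counted non-poor) and an upper bound (all undetermined counted poor).

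The pretreated score needs no change. The cost is a few sentences and a few lines of code, with no imputation. There is one small downside: the poor share among classified patients can still be biased, and can lie further from the truth than without the rule, if laboratory values are missing informatively. The bounds in (c) are there for that reason.
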